**Funding**

None

**Conflict of Interest**

None

Date of the document creation: March 19, 2024

Date of the document update: June 5, 2024

## Design Document and Analysis Plan

### Project Objective

In May 2023, Covered California, California's ACA marketplace, implemented its automatic enrollment program for individuals losing Medicaid coverage, as defined by Senate Bill 260. If individuals are found eligible for subsidized marketplace coverage, individuals will be automatically enrolled in the lowest cost silver plan available to them, but individuals must still take action to confirm their plan or pay their first month's premium. To identify whether the phone outreach is the effective outreach strategy to increase take-up in this population, Covered California implemented this intervention. The results of this evaluation will inform operational and budgeting decisions.

### Target population

The experimental population includes an estimated 60,045 households among consumers who have been discontinued from Medi-Cal, California's Medicaid program, and found eligible for subsidized marketplace coverage.

### Interventions and Randomization

We evaluate the effectiveness of phone outreach on health insurance take-up among auto-enrolled households given that this is a new population for Covered California.

The project's research design is a block-randomized intervention among automatically enrolled households. We separate households by preferred spoken language and net premium of the assigned health plan and randomly assign households within each on continuous basis to (1) a control group with a standard eligibility notice for auto-enrolled households, or to (2) a treatment group to receive additional phone outreach from Covered California's service center.

*Table 1. Approximate sizes of control and treatment groups for the evaluation*

Cohort month	Control	Treatment
August 2023	750	500
September 2023	1,698	5,365
October 2023	7,466	3,132
November 2023	1,838	4,935
December 2023	487	5457
May 2024	6,696	2,021
June 2024	8,000	2,100
July 2024	8,000	2,100
Total	30,101	29,944

### Power:

To arrive at an estimate for the minimum detectable effect (MDE) for our primary outcome, we assume a baseline health insurance take up of 6 percent. The baseline rate was determined with the historical data on the plan effectuation of individuals disenrolled from Medi-Cal in 2018-

2022 years. The intervention was powered at the 80% level to detect a 0.6 percentage point increase in effectuation rate.

### **Likely Effect Size:**

Based on prior phone outreach campaigns carried out by Covered California, we would expect to observe an ITT effect between 0 and 4 percentage points.

### ***Data and Data Structure***

#### **Outcomes:**

We use Covered California administrative data to examine health insurance take-up behavior and health care utilization among households included in the study.

The primary outcome of interest will be a binary indicator for whether a consumer is effectuated into Covered California plan, either the plan assigned through the auto-enrollment process, or into another plan chosen by the consumer by the end of the month at which outreach was conducted.

Our secondary outcomes will be measured 1-2 years after the intervention when data becomes available will include:

1. Tenure with Covered California (measured in months);
2. A binary indicator for whether someone had an office visit during 1-2 years since the intervention;
3. A binary indicator for whether someone had a prescription drug fill during 1-2 years since the intervention;
4. A binary indicator for whether someone had an emergency room visit during 1-2 years since the intervention;
5. A binary indicator for whether someone had a hospital admission 1-2 years before and 1-2 years after the intervention.
6. Total out-of-pocket spending for the 1-2 years since the intervention
7. A binary indicator for whether someone self-reported being uninsured while filing their taxes;

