#### **Data:**

We will use Covered California administrative data to obtain enrollment outcomes and baseline demographics for our sample and health care claims database to obtain health care utilization and financial outcomes.

We will use data from the Department of Health Care Access and Information for hospital admissions data for all individuals in the intervention. We will use data from the California Franchise Tax Board to measure which individuals reported not having Minimum Essential Coverage (MEC) while filing their state taxes.

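### Do controls lack a closing date for the primary outcome, and does the unfixed secondary window give the arms unequal follow-up?

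*Combined protocol and SAP*

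**What the plan says.** The primary outcome (Outcomes section) is effectuation into any Covered California plan "by the end of the month at which outreach was conducted". Under Interventions and Randomization, the comparison arm is "a control group with a standard eligibility notice for auto-enrolled households"; phone calls go only to the treatment arm. Staff "randomly assign households within each on continuous basis", the blocks being language and net premium. Table 1, captioned "Approximate sizes of control and treatment groups for the evaluation", gives both arms a count in each of eight cohort months from August 2023 to July 2024.

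On later outcomes the plan says "Our secondary outcomes will be measured 1-2 years after the intervention when data becomes available". Items 2 to 4 and 6 use a one-to-two-year period since the intervention. Item 5 concerns a "hospital admission 1-2 years before and 1-2 years after the intervention". Item 7 asks whether someone "self-reported being uninsured while filing their taxes", and the Data section sources this from people who "reported not having Minimum Essential Coverage (MEC) while filing their state taxes"; neither place names a tax year.

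The intention-to-treat model under Statistical Models regresses outcome on assignment alone.

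**The concern.** Read literally, the primary cutoff is set by an event that controls never experience. Someone has to choose a date for them, possibly after outcomes are visible. If some treated households were called in the month after their cohort month, the literal rule would also give them a longer window because of treatment, which fits badly with an estimand defined by assignment.

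Small misalignments could matter in a trial this large. The standard error of the difference is about 0.2 percentage points and the design effect is 0.6 points.

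For the secondary outcomes, the treated share differs widely between cohorts. If earlier cohorts were followed for longer, the treated arm as a whole would have more time in which to accrue tenure, visits and spending.

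**Working it through.** **The plan's own figure.** Inputs are 6% baseline take-up, a 0.6-point difference, two-sided alpha 0.05 and the printed Table 1 totals (30,101 control, 29,944 treatment). With pooled variance, power = Φ[(δ − 1.96·SE₀)/SE₁]. Here SE₀ = √[0.063 × 0.937 × (1/30,101 + 1/29,944)] = 0.198 points and SE₁ is also 0.198 points. Power at 0.6 points is 85.7%, and the detectable difference at 80% power is 0.555 points, which rounds to the stated 0.6. The Table 1 rows add to 34,935 and 25,610 rather than the printed totals; with those sums the results are 85.2% and 0.558. The power statement stands and has no bearing on the window.

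**Primary window, natural reading.** If every household in a cohort closes at the end of the cohort month, both arms have the same cutoff and the bias is zero. Continuous assignment gives households different numbers of days before month end. Those days should balance between randomized arms of the same cohort if the allocation ratio is constant within the month.

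**Primary window, misaligned (assumed inputs).** Suppose a fraction f of one arm gains a month in which 1% would effectuate without a call. The bias is f × 1 point. SE at 6% = √[0.06 × 0.94 × (1/34,935 + 1/25,610)] = 0.195 points.

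| f | Bias (points) | Shift in z | Two-sided false-positive rate |
|---|---|---|---|
| 0 | 0 | 0 | 5.0% |
| 5% | 0.05 | 0.26 | 5.8% |
| 10% | 0.10 | 0.51 | 8.1% |
| 20% | 0.20 | 1.02 | 17.6% |

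Neither f nor the 1% comes from the documents. The table shows sensitivity, not an expected error.

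**Secondary window.** Treated share by cohort from the Table 1 rows: August 40.0%, September 76.0%, October 29.6%, November 72.9%, December 91.8%, May 23.2%, June 20.8%, July 20.8%. The overall share is 25,610/60,545 = 42.3%.

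Number the cohort months from August 2023 = 0 to July 2024 = 11. Mean entry month is 252,356/34,935 = 7.22 for controls and 110,551/25,610 = 4.32 for treatment, a gap of 2.91 months. That is the follow-up gap if all households were read at one calendar cut with no upper limit. The plan's window has an upper limit of two years, so follow-up is min(24, cut month − entry month):

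| Assumed common cut | Treated mean (months) | Control mean (months) | Gap |
|---|---|---|---|
| August 2025 | 19.68 | 16.78 | 2.91 |
| December 2025 | 22.54 | 20.06 | 2.47 |
| March 2026 | 23.27 | 22.01 | 1.25 |
| July 2026 | 24.00 | 24.00 | 0 |

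Swapping the two October cells reproduces the printed treatment total of 29,944 but gives 30,601 controls against the printed 30,101, so it does not fully repair the table. With the swap the four gaps are 3.98, 3.24, 1.64 and 0.

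A window that varies by cohort does not by itself create a gap; its length must be associated with treated share. If August alone had 12 extra months, the gap would be 12 × (500/25,610 − 750/34,935) = −0.02 months.

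**Item 5.** The look-back precedes assignment, so the calls cannot affect it.

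**Item 7.** If tax year 2024 were read for everyone (assumed), months remaining in that year after the cohort month average 269,915/25,610 = 10.5 for treatment and 281,740/34,935 = 8.1 for control. Taking the first full tax year after each cohort month does not equalize the arms either: the mean lag to its start is 66,541/25,610 = 2.6 months against 159,736/34,935 = 4.6. The imbalance comes from pooling cohorts with different allocation; naming a year does not remove it.

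**The case for a change.** The best case for a change is that cohort month appears only as a column heading. Nothing ties it to the outcome, and nothing says calls finish within it. A household assigned on the last days of a month could plausibly be called in the next, and a treated household never reached has no literal outreach month at all. The plan expects an effect anywhere from 0 to 4 points, and near zero a bias of 0.1 or 0.2 points could decide significance. On the secondary side, 75.7% of treated households (19,389/25,610) but only 35.0% of controls (12,239/34,935) are in 2023 cohorts, so follow-up that grew with calendar time would favour one arm. A few sentences of text would settle it.

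The description of the text stands: the control cutoff and the exact lengths are unwritten. The harm is not established. No section says that calls fell outside the cohort month, and a treated household that was never reached takes the cohort month like any other. The false-positive rates depend on assumed inputs. The 2.9-month gap needs a single data cut, whereas most of the secondary windows run from the intervention, and it needs a model without a cohort term, which is a separate question about the analysis. The obvious extra wording would not clearly gain much: reporting 24 months only where complete would, before mid-2026, drop the 2024 cohorts and so keep very different fractions of the two arms, and a relative tax-year rule still leaves about 2 months between them.

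**Conclusion.** No change follows. This is an unwritten detail that analysts would fill sensibly: the end of the cohort month for both arms, whether or when a call was made, and an equal window per household for the later outcomes. On that reading the primary bias is zero, provided the cutoff is applied by cohort month and not by call date, and the utilization, admission and spending windows are equal between arms.

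The largest follow-up gap obtainable from Table 1 as printed is about 2.9 months (4.0 with the October cells swapped). It requires one common data cut that the plan does not describe, shrinks as cohorts reach 24 months, and is zero from July 2026. The counts are approximate and the rows do not match the printed totals, so these figures are indicative. The tax outcome is the loosest of the set, but it is secondary, and its imbalance belongs with the question of cohort adjustment.

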### **Statistical Models**

**Intention-to-treat estimation:** To estimate treatment effects, our primary analysis will be an intent-to-treat (ITT) specification, examining the effect of treatment assignment. We will estimate the effect of the treatment using ordinary least squares (OLS) regression. That is, we will regress the outcome of interest (e.g., take-up) for household  $i$  on the treatment indicator:

$$\text{outcome}_i = \alpha + \beta_1 \text{Treatment}_i + \varepsilon_i$$

The coefficient  $\beta_1$  will be the intent-to-treat estimate of the causal effect of the outreach.

**Complier average causal effect estimation:** We will examine the effects of health insurance (among households induced to enroll in a Covered California as a result of random assignment) on our four utilization outcomes. We anticipate a significant share of noncompliers among those households assigned to receive outreach (intervention) as they may have opted out of assigned plan or not enroll into another Covered California plan. Thus, to augment our analysis of insurance take-up, we will also estimate treatment effects based on treatment receipt (enrollment into Covered California Plan), using two-stage least squares regression (2SLS).

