### **Pre-Specified Subgroup Analyses**

We will examine treatment heterogeneity by race and ethnicity of the head of household, written or spoken language, gender of head of household, income group measured by the percentage of the federal poverty level, net premium of assigned plan, age bracket (30 years and younger, 31-49 years old, older than 50 years old), health status as measured by HCIAI discharge data, mixed eligibility household status. Same subgroup analyses will be performed for our complier average causal effect analysis.

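### Secondary outcome 5 is worded as one hospital-admission indicator spanning the periods before and after the intervention, with no rule for combining them; read literally, it does not measure the effect on later admissions

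*Combined protocol and SAP*

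**What the plan says.** All the relevant text is in the combined protocol and SAP.

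- **Outcomes, lead-in to the secondary list:** "Our secondary outcomes will be measured 1-2 years after the intervention when data becomes available will include" the seven items that follow.
- **Outcomes, item 5:** "A binary indicator for whether someone had a hospital admission 1-2 years before and 1-2 years after the intervention".
- **Outcomes, item 4, for comparison:** "whether someone had an emergency room visit during 1-2 years since the intervention". Items 2, 3 and 6 likewise refer only to time since the intervention.
- **Data:** a state source supplies "hospital admissions data for all individuals in the intervention". No window is given. Separately, a claims database is to be used "to obtain health care utilization and financial outcomes".
- **Statistical Models:** the ITT equation regresses the outcome on the treatment indicator alone. The complier analysis estimates effects of insurance "on our four utilization outcomes".
- **Pre-Specified Subgroup Analyses:** one subgroup is "health status as measured by HCIAI discharge data", with no period stated.

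**The concern.** Outreach cannot change an admission that happened before assignment. An outcome that mixes earlier with later admissions therefore answers a different question from whether outreach, or the coverage it induces, changes later hospital use. Item 5 is the only one of the seven secondary outcomes that names a period before the intervention, and it does so inside a single yes/no variable.

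Item 5 probably feeds the complier analysis as well. The Data section separates utilization from financial outcomes, and items 2 to 5 are the only four utilization indicators listed, so they appear to be the four meant. That is an inference from the count. Item 5 is also the only one of those four whose source is said to cover everyone in the study.

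The wording allows several codings: both periods, either period, two separate indicators, or a baseline value plus an outcome. Choosing among them once the data are in hand would weaken the pre-specification.

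**Working it through.** **Plan's own figure.** There is none to reproduce. The plan states no rate, effect or power for outcome 5. The 6 percent baseline and the 0.6 percentage point (pp) detectable effect concern the primary outcome.

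**Step 1: the two one-variable readings.** Let *pre* and *post* be 0/1 indicators of admission before and after assignment.

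| pre | post | both | either | both + either | pre + post |
|---|---|---|---|---|---|
| 0 | 0 | 0 | 0 | 0 | 0 |
| 1 | 0 | 0 | 1 | 1 | 1 |
| 0 | 1 | 0 | 1 | 1 | 1 |
| 1 | 1 | 1 | 1 | 2 | 2 |

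The last two columns agree for every person. Assignment cannot change *pre*, so in expectation ITT(both) + ITT(either) = ITT(post). This needs no admission rate.

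**Step 2: what each reading estimates.** Let q be the share with a prior admission, and d1 and d0 the effects on later admission in people with and without one.

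- ITT(both) = q × d1
- ITT(either) = (1 − q) × d0
- ITT(post) = q × d1 + (1 − q) × d0

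Each reading drops one group. If the two effects share a sign, each reading understates the total. If they differ in sign, a reading can mislead on direction. With assumed values q = 0.08, d0 = −0.30 pp and d1 = +1.00 pp:

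- either: 0.92 × (−0.30) = −0.276 pp
- both: 0.08 × 1.00 = +0.080 pp
- post: −0.276 + 0.080 = −0.196 pp

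**Step 3: the complier estimate.** The 2SLS estimate is the ITT effect on the outcome divided by the ITT effect on enrollment. The denominator does not depend on how outcome 5 is defined, so the estimate shrinks by the same share.

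**Step 4: size, on assumed rates.** Assume a risk q of 5-12%, equal in the two periods, and r = P(post | pre) of 1-3 times q, so r runs from 0.05 to 0.36. Share of the post-only effect retained:

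| Assumption about the effect | both | either |
|---|---|---|
| Same absolute effect in both groups | q | 1 − q |
| Effect proportional to risk | r | 1 − r |
| At q = 0.08, r = 0.24 | 0.08 / 0.24 | 0.92 / 0.76 |
| Whole assumed range | 0.05-0.36 | 0.64-0.95 |

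Under *both*, a share 1 − r of people with a later admission scores 0: 0.64-0.95 over the range.

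**Step 5: illustration.** Assume a true ITT of 0.20 pp and take the top of the plan's expected range for the ITT effect, 4 pp, as the effect on take-up. The complier effect is 0.20 / 0.04 = 5.0 pp. At q = 0.08 and r = 0.24 it would be estimated as 5.0 × 0.08 = 0.4 to 5.0 × 0.24 = 1.2 pp under *both*, and 5.0 × 0.76 = 3.8 to 5.0 × 0.92 = 4.6 pp under *either*. With separate indicators it stays 5.0 pp.

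**The case against.** A reader might infer that item 5 flatly contradicts its own lead-in. The documents do not go that far. The words "Our secondary outcomes will be measured 1-2 years after the intervention" can describe when the data will be collected, and an extract drawn at that time can include earlier admissions. The firm contrast is with the sibling items.

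A reader might also infer that the plan has fixed a wrong estimand. That is too strong. The two one-variable readings are opposites, and because the text says 'and', *either* needs a union-of-windows interpretation. There is also a sensible benign reading. Item 5 has a source covering everyone, and a health-status subgroup would ordinarily be a baseline variable, so admissions before (as health status) and after (as the outcome) would fit together. On that reading there is no dilution. This stands as a plausible intention. However, no section states it, the subgroup section does not link itself to item 5, and the ITT equation has no term for a prior value.

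The sizes are all assumed, and the gain should not be sold as power. In the 0.20 pp illustration, power is only about 15% even for the post-only outcome, against 8-10% under *either* and 5-7% under *both*. What the correction secures is a clear estimand.

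Finally, covariate adjustment does not cure the ambiguity and departs from the plan's unadjusted model. That is fair, so it is offered below only as an option.

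**Conclusion.** The point holds as a defect of definition with minor priority. As worded, outcome 5 is one indicator over two periods with no combining rule. Taken literally as *both*, or less naturally as *either*, it yields one subgroup's weighted effect and not the effect on later admissions. That conclusion rests on algebra alone.

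The retained shares (0.05-0.36 and 0.64-0.95) rest on assumed admission rates, equal risk in the two periods, and the two effect patterns in the table; other rates would give other shares. Under separate indicators the loss is nil.

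It would be wrong to read this as a threat to the trial's validity. Randomization balances prior admissions in expectation, so the test of no effect keeps its Type I error. The primary outcome is untouched, and only one of seven secondary outcomes is involved.

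**What to change.** 1. Define outcome 5 as any hospital admission after assignment, over a stated follow-up window. Reusing the siblings' wording is not quite enough, because 1-2 years does not say whether follow-up is 12 months, 24 months or the second year.
2. List pre-assignment admission separately as a baseline variable, with its own look-back window.
3. State that the health-status subgroup uses pre-assignment discharge data only. Post-assignment discharges could themselves be affected by treatment.
4. Optionally, enter prior admission as a covariate in the outcome 5 ITT and 2SLS regressions. The gain is small: the pre-post correlation is (r − q)/(1 − q) = 0.16/0.92 = 0.174, which squared is about 3% of variance, with 0-7% over the assumed range.

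The cost is one or two lines of wording, best fixed before the admission data are examined. No new source is needed: the plan already obtains admissions for everyone in the study, and item 5 itself names the earlier period.

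### Outcome 6 is labelled total out-of-pocket spending but is taken from claims, so its ITT contrast does not estimate the effect on total out-of-pocket spending

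*Combined protocol and SAP*

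**What the plan says.** The Outcomes section lists seven secondary outcomes, to be measured 1 to 2 years after the intervention. The sixth is "Total out-of-pocket spending for the 1-2 years since the intervention", with no further definition. The Data section names a "health care claims database to obtain health care utilization and financial outcomes". Outcome 6 is the only financial outcome on the list, and no survey, billing or other source of payment data is named. For hospital stays, by contrast, the same section promises "hospital admissions data for all individuals in the intervention".

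Under Statistical Models, "our primary analysis will be an intent-to-treat (ITT) specification, examining the effect of treatment assignment", fitted by OLS at household level. Nothing exempts outcome 6 from this model. Outcome 7 is "A binary indicator for whether someone self-reported being uninsured while filing their taxes", so the plan itself expects some of the sample to be uninsured.

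The plan does not say whose claims the database holds, or how people with no claims are coded.

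**The concern.** Care that an uninsured person pays for in cash produces no claim. When outreach moves such a person into a plan, recorded spending rises from nothing to the plan's cost sharing, while what the person actually pays may rise or fall. The measurement error therefore depends on enrolment, which treatment is designed to change. It differs between arms, and randomisation does not remove it.

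Most of the sample is exposed to this. In the Power section "we assume a baseline health insurance take up of 6 percent", which leaves about 94% of control households outside a Covered California plan. If the variable keeps its present name, a rise in recorded cost sharing could be reported as outreach raising what households pay in total, when total payments were unchanged or lower.

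**Working it through.** **The plan's own figure.** The Power section states that the study is "powered at the 80% level to detect a 0.6 percentage point increase in effectuation rate". With the printed totals of 30,101 and 29,944 households, a 6% baseline and a two-sided 0.05 pooled two-proportion test, the effect detectable at 80% power is 0.555 points, which rounds to 0.6. The cohort rows of Table 1 add to 34,935 and 25,610 instead; those give 0.558, so the discrepancy does not matter here. No design figure is given for outcome 6.

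**Inputs.**
- D, the enrolment effect: 0.6 points (Power) to 4 points, the upper end of Likely Effect Size, where "we would expect to observe an ITT effect between 0 and 4 percentage points".
- u, the share of induced enrollees who would otherwise be uninsured: not given; 1 and 0.5 are used.
- C, cost sharing if enrolled: assumed $400.
- K, cash spending if uninsured: assumed $200 or $700.
- O, out-of-pocket spending under other coverage: assumed $400.

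The algebra assumes that people without claims are entered as $0, that outreach affects spending only by inducing enrolment, that it moves nobody out of a plan, and that the enrolment effect lasts over the spending window.

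**Formulas, per household.**
- True ITT = D × [C − uK − (1−u)O]
- Recorded ITT, Covered California claims only = D × C
- Recorded ITT, all-payer claims = D × [C − (1−u)O]
- Bias, all-payer = D × u × K
- Bias, Covered California claims only = D × u × K + D × (1−u) × O

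**Everyone otherwise uninsured (u = 1).** The two sources then agree.

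| D | Recorded | True, K = $200 | True, K = $700 |
|---|---|---|---|
| 0.6 points | +$2.40 | +$1.20 | -$1.80 |
| 2 points | +$8 | +$4 | -$6 |
| 4 points | +$16 | +$8 | -$12 |

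For example, at 2 points and $700 the true ITT is 0.02 × (400 − 700) = -$6, the recorded ITT is 0.02 × 400 = +$8, and the bias is 0.02 × 700 = $14. The recorded sign is wrong only when K exceeds C. A simulation with K twice C at 4 points agreed with the algebra: true about -$16, recorded about +$16.

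**Half otherwise uninsured (u = 0.5), D = 2 points, K = $700.**
- True: 0.02 × (400 − 350 − 200) = -$3.
- All-payer: 0.02 × (400 − 200) = +$4, bias $7.
- Covered California claims only: 0.02 × 400 = +$8, bias $11. The extra $4 is 0.02 × 0.5 × 400, the unrecorded spending under other coverage.

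**If people without claims are dropped.** Suppose only enrollees remain, D = 4 points, and induced enrollees average $400. If always-enrolled people cost 1.5 times as much, the treatment mean is 400 × (0.06 × 1.5 + 0.04)/0.10 = $520 against $600 in control, a difference of -$80. If they cost half as much, it is 400 × (0.06 × 0.5 + 0.04)/0.10 = $280 against $200, or +$80. Neither is an ITT effect.

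**Could the contrast reach significance?** Assume Covered California claims only, D = 2 points and an SD of $800 among enrollees. The second moment is 400² + 800² = 800,000. The variances are 0.06 × 800,000 − 24² = 47,424 in control and 0.08 × 800,000 − 32² = 62,976 in treatment. The standard error is √(47,424/30,101 + 62,976/29,944) = $1.92, so z = 8/1.92 = 4.2. With an SD of $1,600 the variances are 162,624 and 216,576, the standard error is $3.55 and z is about 2.25. Either would pass the plan's two-sided 0.05 threshold, which carries no multiplicity correction.

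**The case against.** The strongest objection is that the ITT contrast on recorded cost sharing is itself valid. If people outside a plan are zero by definition, the arms are compared as randomised on a well-defined quantity. This stands, and it shapes the fix: the fault lies in the label and the interpretation, and the contrast need not be dropped. Reporting only spending per enrolled month among enrollees would be worse as a comparison, because it conditions on enrolment, which treatment affects.

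It can also be said that the plan's stated objective is take-up, that outcome 6 is one of seven secondary outcomes with no stated hypothesis, and that the two-stage analysis is confined to utilization outcomes. All true. This limits how much is at stake but does not make the label correct.

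A reader might infer three stronger things that the documents do not support:
- That the bias is upward whenever outreach raises enrolment. This needs people without claims to be coded $0, which the plan does not say. With an all-payer source it also needs some induced enrollees to be otherwise uninsured.
- That it makes no difference whose claims the database holds. Cash payments are missed either way, but the size of the bias does depend on coverage ($7 against $11 above).
- That a conclusion about financial protection would be reversed. The plan states no such conclusion, and no document gives spending figures to show that cash spending exceeds cost sharing.

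**Conclusion.** The concern holds in a bounded form. Followed as written, the plan would give an ITT contrast that is not the effect on total out-of-pocket spending. With zero coding the bias is upward: D × u × K, plus D × (1−u) × O if only Covered California claims are held. It is zero if D is zero, or with an all-payer source if no induced enrollee would otherwise be uninsured. If people without claims are dropped, the comparison is no longer ITT and selection bias can go either way.

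With $400 cost sharing, everyone otherwise uninsured and cash spending of $200 to $700, the bias is $1.20 to $4.20 per household at 0.6 points and $8 to $28 at 4 points. The dollar figures are assumptions. The existence of the bias does not depend on them, but its size and any sign reversal do. Office visits, drug fills and emergency visits appear to rest on the same claims source and need a similar check; this point is limited to outcome 6, where the word total claims more than the data can show.

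**What to change.** Under Outcomes, rename outcome 6 as cost sharing recorded in Covered California plan claims, and set people and months outside such a plan to $0 by definition. Under Data, state whose claims the database holds. Under Statistical Models, keep the ITT contrast on this quantity for all randomised households, and state that it is not read as an effect on total out-of-pocket spending or on financial protection. Any figure per enrolled month among enrollees should be marked as descriptive and not compared between arms as an effect.

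This takes a few sentences and no new data. Because the outcome is measured 1 to 2 years after the intervention, the change can be made before analysis. The downside is that the secondary outcome supports a narrower conclusion. If the sponsor wants the effect on total spending, a source covering payments by everyone randomised would have to be added.
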